### 12.2.1 ANALYSIS POPULATION

All eligible subjects will be included in the statistical analyses. Statistical analyses will be conducted based on intention-to-treat (ITT) principle.

### 12.3 DETERMINATION OF SAMPLE SIZE

The power calculation (and thus the sample size) is based on the assumption that the data are approximately normally distributed. We assume that the patient size in both treatment groups will be the same, 1:1. Based on previous studies and unpublished data from the U-PAIN cohort we assume that the baseline value (index visit) for the primary outcome is 6,0 in both treatment groups. We consider a difference in change of 1,0 between the groups at 12 months to be clinically relevant and assume that the standard deviation of the change is 1,43. To detect a difference of 1.0 in pain interference between the two groups with a power of 90% and a type-1 error of 5%, 46 participants in each treatment group is required. With regard to dropouts (20%) we aim for at least 55 participants per treatment group (110 in total). Based on the current patient count calculation (90% power and  $\alpha = 0.05$  to detect a 1.0 difference in the primary outcome measure) based on previous studies (16) and data from the U-PAIN cohort (28), we aim in the intervention study for at least 55 study participants per treatment group (110 in total).

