## **6 TRIAL DESIGN AND SETTING**

### **6.1 TRIAL OUTLINE**

The trial is a controlled before-and-after study that has been designed, and will be reported, according to the applicable CONSORT guidelines (19). No randomization or blinding will be involved. A feasibility study will be conducted prior to the full trial.

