### **6.2 SETTING AND SITE SELECTION**

This study will be conducted at eight healthcare centres in Region Uppsala, NVH. At four of the healthcare centres a new person-centred team-based treatment model including pharmacists (intervention) will be implemented. Basic conditions for these healthcare centres are the accessibility of at least one person of each healthcare profession: pharmacist, GP, psychologist and physiotherapist, where one of these (or a rehabilitation coordinator or a nurse) takes the role of care manager. Healthcare personnel will receive special training in person-centered care and managing patients diagnosed with chronic pain before the study. In addition, four control healthcare centres without a pharmacist will be matched with the intervention healthcare centres

according to according to geographic area (urban, suburban, or rural) and the size of the centres (number of listed patients). No specific efforts for implementation will be made in these control centres.

Patients being participants at the intervention health care centres will start their inclusion in the new person-centred team-based treatment immediately at the index appointment and up to 24 weeks. Participants at the control centres will receive usual care.

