### 6.3 STAFF TRAINING AND IMPLEMENTATION

All personnel involved in the study (GPs, physiotherapists, psychologists (or social workers), pharmacists including the care manager) will participate in two half day-sessions of training. In addition to the two half-day sessions, the care managers (i.e. one in the team above, a rehabilitation coordinator or a nurse) will receive additionally two hours of training in providing person-centred and team-based care. The education focuses on optimized diagnostics and treatment of pain according to the biopsychosocial model including pharmacological aspects. The training includes interactive and case-based lectures on chronic pain, opioids, person-centred care and teamwork. The training will be held locally at each healthcare centre and be arranged by persons from the research group in collaboration with a psychologist and a physiotherapist from the Pain Clinic, Uppsala Academic Hospital. Further, the training will include information about the study. To ensure an adequate pain analysis the personnel involved will also receive instructions about how to document relevant findings in the patients' electronic health recordings. To avoid duplication of work and overlaps at the various care visits, checklists will be created for each profession respectively, to result in coordinated documentation.

It is the responsibility of the investigators to ensure that all personnel involved in the trial are fully informed of all relevant aspects of the trial, including detailed knowledge of and training in all procedures to be followed.

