### 12.2 STATISTICAL ANALYSIS

Primarily, statistical analyses will be conducted based on intention-to-treat (ITT) principle. Patient characteristics will be presented descriptively per treatment group. The average value of pain interference and quality of life in accordance with BPI-SF will be calculated and analyzed separately per treatment group. The difference between the intervention group and the control group will be analysed through regression analysis including the ability to adjust for base line data and other covariates. ANOVA for repeated measurements will be used to analyse the average differences between the two groups until 12 months. The number of dropouts will be reported and analysed descriptively. All randomized study subjects completing the whole study period (complete cases) will be analyzed Per Protocol. For a specific analysis, study subjects with missing data on any of the variables in the model will be excluded from the analysis. Analyses of this population is seen as sensitivity analysis to investigate whether conclusions are sensitive to assumptions regarding the pattern of missing data. All analyses will be described in a prespecified statistical analysis plan (SAP). Significance tests will be two-tailed and a p-value less than 0.5 will be interpreted as significant. All statistical analyses are carried out in an SPSS, SAS or R. The process evaluation is analysed descriptively as well as through a qualitative thematic analysis.

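### Treatment is assigned to eight healthcare centres, but the sample size and the named analyses treat patients as independent, so the 90% power and the 5% error rate are not supported

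*Protocol*

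**What the plan says.** Protocol section 6.2 sets treatment at the level of the centre: "At four of the healthcare centres a new person-centred team-based treatment model including pharmacists (intervention) will be implemented", and "four control healthcare centres without a pharmacist will be matched with the intervention healthcare centres". Section 6.1 adds "No randomization or blinding will be involved". Every participant at a centre therefore receives that centre's arm. Under section 6.3 the staff are prepared centre by centre: "The training will be held locally at each healthcare centre".

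Section 12.3 bases the sample size on approximate normality, equal groups, an SD of change of 1.43 and this target: "We consider a difference in change of 1,0 between the groups at 12 months to be clinically relevant". It concludes that "with a power of 90% and a type-1 error of 5%, 46 participants in each treatment group is required", raised to 55 per group (110 in total) for 20% dropout. It mentions no ICC, design effect or number of centres.

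Section 12.2 names a regression that can adjust for baseline and other covariates, and then "ANOVA for repeated measurements will be used to analyse the average differences between the two groups until 12 months". It defers detail to a statistical analysis plan, which is not available here. Clustering is not mentioned anywhere in the protocol.

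**The concern.** Patients at one centre share prescribers, local routines and, in the intervention arm, one trained team and its care manager. Their changes in pain interference are likely to be more alike than those of patients from different centres. The treatment contrast is a contrast between centres, so between-centre variation enters its standard error in full. With four centres per arm, that variation is estimated on 8 − 2 = 6 degrees of freedom, not on the 90 that 46 patients per arm would suggest.

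Two things are at stake. If the analysis ignores centre, the standard error is too small, and an ordinary difference between centres can be reported as a treatment effect more often than the stated 5%. If the analysis respects the design, the trial does not have the power claimed for it. Repeated-measures ANOVA does not help, because it handles correlation between visits of the same patient and not between patients of the same centre.

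**Working it through.** **Inputs.** From section 12.3: difference 1.0, SD of change 1.43, type I error 5%, power 90%, 46 analysed per arm, 20% dropout. From section 12.2: two-tailed tests. From section 6.2: four centres per arm. Assumed, because the protocol gives none: ICC of the change score 0.01 to 0.10.

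**Step 1: reproduce the stated figure.** For independent patients, n per arm = 2 × [1.43 × (1.960 + 1.282) / 1.0]² = 42.97, so 43. The t-based version gives 44. Power at 46 per arm is 91.8% (normal) or 91.3% (t). The stated 46 is thus the independent-patients answer with a margin of two or three patients, and it contains no real allowance for centres.

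**Step 2: add the centres.** Patients per centre: m = 46/4 = 11.5. Design effect: DE = 1 + (m − 1) × ICC. Standard error: SE = 1.43 × √(2 × DE / 46), which is 0.298 when DE = 1. Power on 6 df comes from the noncentral t with noncentrality 1.0/SE and critical value 2.447. The type I error of a test that ignores centre is 2Φ(−1.96/√DE).

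| ICC | DE | SE | Power, design effect only (normal) | Power, 6 df | Type I error ignoring centre |
|---|---|---|---|---|---|
| 0 | 1.00 | 0.298 | 91.8% | 79.7% | 5.0% |
| 0.01 | 1.105 | 0.313 | 89.1% | 75.8% | 6.2% |
| 0.02 | 1.21 | 0.328 | 86.2% | 72.0% | 7.5% |
| 0.05 | 1.525 | 0.368 | 77.5% | 62.2% | 11.2% |
| 0.10 | 2.05 | 0.427 | 64.9% | 50.2% | 17.1% |

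A simulation with 40,000 replicates and centres of 12, 12, 11 and 11 patients per arm gave type I errors of 6.1%, 7.5%, 11.5% and 17.6% at ICCs of 0.01, 0.02, 0.05 and 0.10, in line with the formula.

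**Step 3: effect on the confidence interval.** Ignoring centre, the 95% half-width is 1.987 × 0.298 = 0.59. On 6 df it is 2.447 × SE, or 0.77, 0.90 and 1.04 at ICCs of 0.01, 0.05 and 0.10. At the last value the half-width exceeds the target difference itself.

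**Step 4: sensitivity to the number analysed.** A 20% loss from 55 leaves 44 per arm, with 6-df power of 74%, 61% and 50% at ICCs of 0.01, 0.05 and 0.10. If all 55 were analysed it would be 82%, 67% and 53%.

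**Step 5: can more patients restore 90%?** On 6 df with four centres per arm, 90% needs 74, 90 and 274 analysed per arm at ICCs of 0.01, 0.02 and 0.05. At ICC 0.10 no number is enough. With unlimited patients per centre, SE = 1.43 × √(2 × 0.10 / 4) = 0.320, and power stops at about 74%.

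**The case against.** The strongest reply concerns the p-values. Section 12.2 names only broad methods and leaves detail to an analysis plan that is not shown. That plan could add a random centre effect, so the inflated error rates apply to the methods as named and not necessarily to the final analysis. This stands as a condition. It does not rescue section 12.3, whose 90% is stated without qualification in the protocol. Nor does the allowance for other covariates cover the gap: centre is nested in arm, so fixed centre effects cannot be estimated together with the treatment effect.

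The ICC is also unknown and may be small. By design effect alone the loss at ICC 0.01 is slight (89.1%), and with all 55 per arm analysed power is still 90.5% at ICC 0.02. That is fair, but those figures use a normal reference that eight centres do not support. On 6 df the same two cases give 75.8% and 77.8%. The shared-team argument is also weaker for the usual-care centres.

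The power figures use the SD of the raw change, whereas a baseline-adjusted analysis would be more precise. If the baseline to follow-up correlation were 0.5 (an assumption), the residual SD would be 1.43 × √0.75 = 1.24, and 6-df power at 46 per arm would be about 86%, 74% and 62% at ICCs of 0.01, 0.05 and 0.10. This softens the loss without removing it.

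Finally, the centres are matched. An analysis in four pairs has 3 df, not 6, and would lose further power unless the matching removed enough between-centre variation to compensate.

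**Conclusion.** The point holds. Assignment by centre and the independent-patients origin of the 46 both follow from the protocol alone. At the protocol's own SD and difference with 46 analysed per arm, a valid 6-df test has about 76% power at ICC 0.01, 62% at 0.05 and 50% at 0.10, and about 80% even with no within-centre correlation. The methods named in section 12.2, used as written, have a true type I error of about 6% to 17% over the same range, unless the analysis plan models centre. The exact size rests on the assumed ICC, on equal centre sizes and on an unpaired analysis of an unadjusted change score. Baseline adjustment could recover part of the loss. Because the standard error, interval and p-value of the primary comparison all depend on this, it should be corrected before the full trial starts. There is room to do so: section 10.1 foresees updating the protocol after the feasibility study, and section 13.3 requires ethical approval of the final version.

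**What to change.** **Section 12.2.** Name as primary analysis a linear mixed model for pain interference with baseline as a covariate, a patient-level term for the repeated visits, a random centre intercept, and Kenward-Roger or Satterthwaite degrees of freedom. A comparison of the eight baseline-adjusted centre means on 6 df is an equivalent and simpler choice. Say whether the matching of centres enters the analysis and, if it does, that the degrees of freedom fall to 3. Do not use fixed centre effects.

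**Section 12.3.** Replace the unqualified 90% with the power that 55 recruited per arm in four centres per arm provides over a stated ICC range, giving the number expected to be analysed and any assumed gain from baseline adjustment.

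**Cost.** Wording in two sections, with no added patients and no change to treatment. The stated power becomes less favourable and the reported interval wider. The rewording makes the claims honest but does not restore 90%; at the higher ICCs only more centres, not more patients per centre, could do that.

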## 13 ETHICS

### 13.1 ETHICAL CONSIDERATIONS

The trial will be conducted in accordance with the protocol, applicable regulatory requirements and the ethical principles of the Declaration of Helsinki as adopted by the 18th World Medical Assembly in Helsinki, Finland, in 1964 and subsequent versions.

The risks of participating in the project are considered low. Treatment and assessment of the study participants in the feasibility as well as in the intervention study will deviate from current practice and may affect the participant's physical and psychological health. A reduction in opioids may become relevant among some of the study participants which may affect them and lead to temporary symptoms of abstinence and increased pain. However, it is important to emphasize that treatment and assessment will follow current guidelines of chronic pain and current guidelines of opioid tapering.

The participants in the study will be in a position of dependence on the healthcare providers. However, this will not significantly deviate to the patient-staff relation in usual care. Furthermore, the study participants will be informed both verbally and in writing that they may withdraw their participation from the study whenever they want and that a withdrawal will not affect the usual care provided.

The project may lead to improved treatment of chronic pain in primary healthcare. An ethical problem may appear if the intervention is effective, but resources are too demanding, or that it displaces resources from other patient groups. As in many other situations, priorities of healthcare resources must then be made according to resources available.

### 13.2 SUBJECT INFORMATION AND INFORMED CONSENT

It is the responsibility of the Investigator to provide each subject with full and adequate verbal and written information about the objectives, procedures and possible risks and benefits of the trial. All subjects will be given the opportunity to ask questions about the trial and will be given sufficient time to decide whether or not to participate in the trial. The written subject information must not be changed without prior discussion with the Sponsor.

The subjects will be notified of their voluntary participation and of their freedom to withdraw from the trial at any time and without giving any particular reason. Subjects must also be informed that withdrawing from the trial will not affect their future medical care, treatment or benefits to which the subject is otherwise entitled.

The Investigator is responsible for obtaining written Informed Consent from all subjects (or their legally acceptable representatives and/or witnesses, where applicable) prior to enrolment in the trial.

The subjects will consent to:

- Participating in the trial.
- Sponsor representatives and regulatory authorities gaining full access to electronic health records, to verify the accuracy of the data collected in the trial.
- Recording, collection and processing of data and storing of data in a database.

It should be clearly stated that the data will not identify any subject taking part in the trial, in accordance with the Regulation (EU) 2016/679 (General Data Protection Regulation, GDPR).

A copy of the subject information and the Informed Consent form will be given to the subject. The Investigator (or the designated representative) who gave the verbal and written information to the subject will sign the Informed Consent form. The Investigator will file the signed Informed Consent forms in the Investigator's File for possible future audits and inspections.

### 13.3 ETHICAL REVIEW OF THE TRIAL

The feasibility study of this trial has received ethical approval from the Swedish Ethical Review Authority (registration number 2023-00313-01, date: 2023-04-23). The final version of the trial protocol and subject information must be approved by the Swedish Ethical Review Authority before the full trial can be conducted.

## **14 DATA HANDLING AND RECORD KEEPING**

### **14.1 CASE REPORT FORMS**

Case report forms will be completed for each included subject as detailed in the Data Management Plan ([Appendix XX](#)). The subject's identity must always remain confidential.

## **15 INSURANCE**

The subjects are insured through the Swedish Social Insurance Agency (Försäkringskassan) and the Swedish Patient Insurance (Landstingens Ömsesidiga Försäkringsbolag) as part of standard health care.

## **16 TRIAL END OR TERMINATION**

### **16.1 END OF TRIAL**

The trial ends when the last subject has completed the last follow-up.

### **16.2 CRITERIA FOR TERMINATION OF THE TRIAL**

The Sponsor reserves the right to discontinue the trial prior to inclusion of the intended number of subjects, but intends to exercise this right only for valid scientific or administrative reasons. After such a decision, all CRFs must be completed as far as possible.

The trial can be prematurely discontinued in the following cases (examples):

- Trial protocol is difficult to cope with.
- Recruitment of eligible subjects is far too low.
- Unacceptable low Investigator, Sponsor or subject compliance.
- Critical change in personnel, administrative or scientific standards at the Sponsor or at the trial centre.
- No significant result will be obtained as anticipated.

## 18 APPENDICES

*Include the following optional appendices, if applicable:*
